9.5.2.2 Laboratory data

The summary of laboratory evaluations will be presented for three groups of laboratory tests (hematology, serum chemistry and urinalysis). Descriptive summary statistics for the change from Baseline to each study visit will be presented.

These descriptive summaries will be presented by test group, laboratory test and treatment group. Change from Baseline will only be summarized for patients with both Baseline and Post-Baseline assessments.

For each parameter, the maximum change from Baseline within each study period will be analyzed analogously.

9.5.2.3 Vital signs

Analysis of the vital sign measurements using summary statistics for the change from Baseline for each Post-Baseline visit will be performed. These descriptive summaries will be presented by vital sign and treatment group. Change from Baseline will only be summarized for patients with both Baseline and Post-Baseline values.

9.7 Interim analyses

Once all data until/including Week 24 (containing the primary and secondary endpoints) are complete and clean, the database for that study period may be locked and analyzed. The results may be published or made available to personnel involved in data collection of this study prior to database lock of the complete study period until Week 52.

9.8 Sample size calculation

The primary endpoint of this trial is the percentage of patients with resolution of Achilles tendon enthesitis assessed by application of firm pressure with the pulp of the thumb by the physician at Week 24. The sample size calculation is based on the same enthesitis assessment we performed within the FUTURE 2 PsA trial (CAIN457F2312) in the form of the LEI which is composed of three different enthesial sites (Lateral epicondyle, left and right; Medial femoral condyle, left and right; Achilles tendon insertion, left and right). Within this trial, the resolution of enthesitis amongst those patients with these symptoms at Baseline has been assessed for Week 24:

Week 24, the end of the placebo-controlled phase:

- Secukinumab (300 mg): 48.2% of patients.
- Secukinumab (150 mg): 42.2% of patients.
- Placebo: 21.5% of patients.

In addition to these clinical data we can make the following assumptions:

- There is no difference in response to secukinumab between the different enthesial sites assessed as part of the LEI in the FUTURE 2 trial. Therefore we do not expect a different response when we only assess the Achilles tendon insertion.
- There is no difference in secukinumab response rates regarding resolution of enthesitis between PsA and axPsA patients. Therefore we pool the analysis for both diseases.

A total of 89 patients per arm are required to achieve 90% power to detect a difference on a two-sided, 5% significance level, if the true response rates are 45% under secukinumab and 21% under placebo. To account for some drop-outs and other protocol violations, 100 patients per arm = 200 patients total should be recruited into this trial.

For the comparison within the 2 subgroups of PsA and axSpA patients, which will consist of approximately 50% of the total study population each, the trial will have about 58% power with regard to the primary endpoint.

10 Ethical considerations

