9.1 Analysis sets

The following analysis sets will be used in this trial:

Randomized set: The randomized set will be defined as all patients who were randomized. Unless otherwise specified, miss-randomized patients (miss-randomized in IRT) will be excluded from the randomized set.

Full analysis set (FAS): The FAS will be comprised of all patients from the randomized set to whom study treatment has been assigned. Following the intent-to-treat principle, patients will be evaluated according to the treatment assigned to at randomization. For patients randomized erroneously into the wrong stratum, the actual stratum will be used for analyses.

Safety set: The safety set includes all patients who took at least one dose of study treatment during the treatment period. Patients will be evaluated according to treatment received.

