### 2.5.1 Primary endpoint

The primary endpoint is the percentage of patients with resolution of Achilles tendon enthesitis as assessed by the respective subcomponent of the LEI at Week 24. This resolution is referred to as 'response' below.

The analysis of the primary efficacy variable will be based on the FAS.

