### 2.5.3 Handling of missing values/censoring/discontinuations

This study aims to estimate the magnitude of treatment effects that are obtainable under the respective treatments. The disease activity is expected to decrease in the course of treatment. If a patient drops out or discontinues the trial prematurely, the last observed value of that patient seems to be a proper estimate for the effect achieved in that patient.

For the primary endpoint, a patient with a missing assessment will be considered as a responder if he/she has met the response criterion already at the time of drop-out. Otherwise he/she will be considered as a non-responder.

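### The 58% subgroup power in protocol 9.8 fits a conservative test on about 42–44 patients per arm; the planned logistic regression on about 50 per arm of the FAS has about 64–72%

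*Protocol*

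**What the plan says.** Protocol 9.8 sizes the trial as follows: "A total of 89 patients per arm are required to achieve 90% power to detect a difference on a two-sided, 5% significance level". The planning rates are 45% (active) and 21% (placebo). To allow for drop-outs and protocol violations it then states that "100 patients per arm = 200 patients total should be recruited into this trial". Of the two disease subgroups, "which will consist of approximately 50% of the total study population each", it says that "the trial will have about 58% power with regard to the primary endpoint". It names neither the test nor the number per arm behind that figure.

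The analysis is set out elsewhere:

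- **Model.** Logistic regression (protocol 9.4.2, SAP 2.5.2), with the same model in each subgroup (protocol 9.5.1.6; the SAP drops the diagnosis factor there).
- **Level.** After rejection in the overall population, each subgroup is tested at 0.05 as part of the confirmatory strategy (protocol 9.5.1.7, SAP 2.5.2).
- **Population.** "The analysis of the primary efficacy variable will be based on the FAS" (SAP 2.5.1). Protocol 9.1 defines that set: "The FAS will be comprised of all patients from the randomized set to whom study treatment has been assigned".
- **Missing Week 24 result.** Under SAP 2.5.3, "a patient with a missing assessment will be considered as a responder if he/she has met the response criterion" by the time of drop-out, and as a non-responder otherwise. Protocol 9.4.3 has the same rule.

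SAP section 3 repeats the 89 per arm and the 45% and 21%, but at a two-sided 2.5% level and with 46% subgroup power.

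**The concern.** Half of 100 per arm is 50 per arm in each subgroup, and the missing-data rule keeps drop-outs in the denominator. At the stated rates and level, an uncorrected test on 50 per arm has clearly more than 58% power. So the figure seems to describe a different test on a smaller number of patients.

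The subgroup tests are confirmatory, and their stated power is context for a non-significant PsA or axSpA result. If it is understated, such a result looks less informative than it is. The protocol and SAP also give different figures, and because neither states its basis, a reader cannot tell which one to use.

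**Working it through.** **Inputs.** p1 = 0.45, p0 = 0.21, two-sided alpha 0.05, 89 required and 100 randomised per arm, subgroups about half each (protocol 9.8); 1:1 allocation (protocol 3.1); subgroup alpha 0.05 (protocol 9.5.1.7). Hence d = 0.24 and the mean rate is 0.33. Subgroup n per arm is 100/2 = 50 as randomised, or 89/2 = 44.5 (taken as 44) on the required number.

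**1. Reproducing 58%.** The uncorrected two-proportion formula is

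power = Φ{[d√n − 1.960·√(2·0.33·0.67)] / √(0.45·0.55 + 0.21·0.79)} = Φ{[0.24√n − 1.960·0.6650] / 0.6430}.

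The continuity-corrected version replaces n by n′ = n − 2/d + 1/(n·d²). For n = 44, n′ = 44 − 8.33 + 0.39 = 36.06, so power = Φ{(1.441 − 1.303)/0.6430} = Φ(0.214) = **58.5%**. Fisher's exact test, enumerated over all binomial outcomes, gives 57.8% on 42, 59.3% on 43 and 59.9% on 44 per arm. Either test on about 42–44 per arm is consistent with 58%.

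The same family of tests fits the 89. The uncorrected requirement for 90% power is N = [(1.960·0.6650 + 1.282·0.6430)/0.24]² = 78.6, so 79. With the correction, (N/4)·[1 + √(1 + 4/(N·d))]² = 86.7, so 87, which is close to 89 but not equal to it.

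It also fits the SAP: at two-sided 2.5% the corrected formula gives 45.7% on 43 and 47.0% on 44 per arm, against the stated 46%.

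**2. The planned test.** For each pair of responder counts I took the log odds ratio over its standard error (the unadjusted Wald logistic test), rejected above 1.960, and summed the binomial probabilities. All rows are at two-sided 5%, 45% against 21%.

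| Test | 44 per arm | 50 per arm |
|---|---|---|
| Continuity-corrected formula | 58.5% | 65.3% |
| Fisher exact | 59.9% | 66.2% |
| Wald logistic (planned test) | 68.1% | **72.2%** |
| Uncorrected chi-square, exact enumeration | 69.1% | 73.2% |

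Adjustment changes little. Simulated power on 50 per arm is about 71.6% with a TNF-status covariate and 70.9% with a four-level country factor (covariate mix assumed). Requiring overall rejection first gives 71.6%.

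**3. Allowing for drop-outs.** The increase from 89 to 100 implies 11 of 100, or 11%, lost per arm. Assume that all of them count as non-responders. The rates become 0.45·0.89 = 0.4005 and 0.21·0.89 = 0.1869, and the Wald logistic test on 50 per arm has **64.4%** power.

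**4. Distance from 58%.** 72.2 − 58 = 14 points with no loss; 64.4 − 58 = 6 points with 11% non-responders.

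**5. Overall comparison.** The Wald logistic test has 93.2% power at 89 per arm and 95.5% at 100 with no loss. At 100 per arm with 11% non-responders it has 92.0%.

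**The case against.** The strongest reply is that 58% is a legitimate planning figure. Section 9.8 treats 89 as the number needed and the extra 11 as an allowance for loss, so halving 89 carries that basis into the subgroups. Sizing with a conservative approximation and analysing by logistic regression is common. A subgroup result will in any case be read mainly from its odds ratio and confidence interval, and nothing about the test, the level or the decision rule changes.

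Much of this stands. The figure reproduces, it errs on the safe side, and the trial is large enough. What does not stand is that it describes the planned analysis: even on 44 per arm the planned test has 68%.

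Three stronger readings are tempting, and the documents do not support them.

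- **That 58% is an arithmetic error, or can come only from a continuity-corrected test on 44 per arm.** Fisher's test on 42–44 fits as well. So, outside the protocol's stated inputs, do an uncorrected test at the SAP's 2.5% on 44 per arm (56.3% pooled, 59.3% unpooled) and the logistic test on 50 per arm with the quoted 42.2% and 21.5% (59.5%). The method cannot be identified from the text.
- **That no standard test on 50 per arm gives 58%.** This holds only with no loss. With 11% non-responders, Fisher's test on 50 per arm gives 58.3%.
- **That subgroup power simply is 72%, 14 points above the stated figure.** The 72% gives every drop-out the full response rate, so it is the top of the range.

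**Conclusion.** The point holds in limited form. The 58% matches a conservative test on about 42–44 patients per arm, and section 9.8 states neither the test nor the number. For the analysis the plan specifies, power at the protocol's own rates and level is about 72% with no loss and about 64% if 11% of each arm all become non-responders. The stated figure is therefore about 6 to 14 points too low.

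The range rests on the stated 45% and 21% applying in both diseases, an even split of diagnoses, and an 11% loss inferred from the step from 89 to 100. Counting all of that loss as non-response is an assumption and a pessimistic one, because patients who had already responded at drop-out are kept as responders.

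The consequence is for documentation and interpretation. The sample size is adequate.

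**What to change.** In protocol 9.8 and SAP section 3:

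- Name the test, the number per arm and the alpha behind each power figure.
- Restate subgroup power for the planned logistic regression on the FAS as about 64–72% on about 50 per arm. Show that the upper value assumes no loss and the lower one 11% of each arm counted as non-responders. The 72% should not stand alone.
- Restate overall power as about 93% at 89 and 95% at 100 per arm with no loss, and about 92% at 100 with 11% non-responders.

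In the SAP, first reconcile the two-sided 2.5% level and the 46% with the 0.05 level at which both documents test the subgroups. Putting the new range next to the 2.5% would create a fresh contradiction.

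The cost is one paragraph in each document, with no change in enrolment or analysis.

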10.1 Regulatory and ethical compliance

This clinical study was designed and shall be implemented, executed and reported in accordance with the ICH Harmonized Tripartite Guidelines for Good Clinical Practice, with applicable local regulations (including European Directive 2001/20/EC, US CFR 21, and Japanese Ministry of Health, Labor, and Welfare), and with the ethical principles laid down in the Declaration of Helsinki.

10.2 Informed consent procedures

Eligible patients/subjects may only be included in the study after providing written (witnessed, where required by law or regulation), IRB/IEC-approved informed consent, or, if incapable of doing so, after such consent has been provided by a legally acceptable representative(s) of the patient. In cases where the patient's representative gives consent, the patient must be informed about the study to the extent possible given his/her understanding. If the patient is capable of doing so, he/she must indicate assent by personally signing and dating the written informed consent document or a separate assent form. Informed consent must be obtained before conducting any study-specific procedures (e.g. all of the procedures described in the protocol). The process of obtaining informed consent must be documented in the patient source documents.

Novartis will provide to investigators in a separate document a proposed informed consent form that complies with the ICH GCP guideline and regulatory requirements and is considered appropriate for this study. Any changes to the proposed consent form suggested by the investigator must be agreed to by Novartis before submission to the IRB/IEC, and a copy of the approved version must be provided to the Novartis monitor after IRB/IEC approval.

Women of child bearing potential must be informed that taking the study treatment may involve unknown risks to the fetus if pregnancy were to occur during the study and agree that in order to participate in the study they must adhere to the contraception requirement for the duration of the study. If there is any question that the patient will not reliably comply, they must not be entered in the study.

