Study design	This is a 52-week, randomized, parallel-group, double-blind, multicenter, international study consisting of a 10-week screening period, a 24-week, placebo-controlled, double-blind treatment period and a 28-week open-label treatment period.
Population	The study population will consist of male and female patients (≥ 18 years old at the time of consent) with active PsA or axSpA presenting active enthesitis including one Achilles tendon site that is refractory to standard treatment. The Achilles tendon enthesitis must be clinically diagnosed and must be MRI-positive according to the investigator's judgement.
Key Inclusion criteria	 Patients eligible for inclusion in this study have to fulfill all of the following key inclusion criteria (please refer Section 4.1 for complete list): Male or non-pregnant, non-lactating female patients at least 18 years of age. PsA patients must fulfill the following criteria: Diagnosis of PsA classified by CASPAR criteria with symptoms for at least 6 months and Active PsA as assessed by ≥ 1 tender joints out of 78 and ≥ 1 swollen joints out of 76 at Baseline (dactylitis of a digit counts as one joint each). AxSpA patients must fulfill the following criteria: AxSpA patients must fulfill the following criteria: AxSpA patients must fulfill the following criteria: AxSpA as per the classification of the ASAS axSpA criteria with objective signs of inflammation at Screening, evident by either MRI with Sacroiliac joint inflammation or definite radiographic sacroilitis according to the modified NY criteria (both according to source documentation) and/or hsCRP > ULN (as defined by central lab) and Active disease assessed by total BASDAI ≥ 4 (0–10) at Baseline. Diagnosis of Achilles tendon enthesitis according to swelling and tenderness at the insertional site of the Achilles tendon into the calcaneus. Onset of heel pain ≥ 1 month at Baseline. Heel enthesitis that is MRI-positive according to the investigator's judgement. Patients who have been exposed to up to two TNFα inhibitors. Patients who have previously been on a TNFα inhibitor will be allowed enter into study after an appropriate wash-out period prior to

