- Women of child-bearing potential, defined as all women physiologically capable of becoming pregnant, unless they are using effective methods of contraception during dosing of study treatment and minimum 16 weeks or longer if local label requires it (e.g. 20 weeks in EU) after stopping the study medication. Effective contraception methods include:
 - Total abstinence (when this is in line with the preferred and usual lifestyle of the subject). Periodic abstinence (e.g., calendar, ovulation, symptothermal, post-ovulation methods) and withdrawal are not acceptable methods of contraception
 - Female sterilization (have had surgical bilateral oophorectomy with or without hysterectomy) total hysterectomy or tubal ligation at least 6 weeks before taking investigational drug. In case of oophorectomy alone, only when the reproductive status of the woman has been confirmed by follow up hormone level assessment
 - Male sterilization (at least 6 months prior to screening). For female subjects on the study, the vasectomized male partner should be the sole partner for that subject
 - Barrier methods of contraception: condom or occlusive cap (diaphragm or cervical/vault caps) with spermicidal foam/gel/film/cream/ vaginal suppository.
 - Use of oral, (estrogen and progesterone), injected or implanted hormonal methods of contraception or placement of an intrauterine device (IUD) or intrauterine system (IUS) or other forms of hormonal contraception that have comparable efficacy (failure rate <1%), for example hormone vaginal ring or transdermal hormone contraception

In case of use of oral contraception women should have been stable on the same pill for a minimum of 3 months before taking investigational drug.

Women are considered post-menopausal and not of child bearing potential if they have had 12 months of natural (spontaneous) amenorrhea with an appropriate clinical profile (e.g. age

appropriate, history of vasomotor symptoms) or have had surgical bilateral oophorectomy (with or without hysterectomy), total hysterectomy or tubal ligation at least 6 weeks ago. In the case of oophorectomy alone, only when the reproductive status of the woman has been confirmed by follow up hormone level assessment is she considered not of child bearing potential.

- 14. Active ongoing inflammatory diseases other than PsA and axSpA that might confound the evaluation of the benefit of secukinumab therapy, including inflammatory bowel disease or uveitis.

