5.2 Treatment arms

Patients will be randomized to one of the following 2 treatment groups in a 1:1 ratio as depicted below:

- Group 1: secukinumab 150 mg/300 mg s.c.: secukinumab as 1 (1.0 mL PFS of 150 mg dose) s.c. or 2 (2 × 1.0 mL PFS of 150 mg dose, 300 mg) s.c. injections at Baseline, Weeks 1, 2, and 3, followed by administration every 4 weeks starting at Week 4.
 - PsA patients, who have been previously exposed to TNF blockers, and/or with concomitant moderate to severe plaque psoriasis receive 2 (two) 1.0 mL PFS of 150 mg dose (i.e. 300 mg) s.c..
 - Other PsA patients and axSpA patients receive 1 (one) 1.0 mL PFS of 150 mg dose s.c..
- Group 2: placebo s.c. followed by secukinumab 150 mg/300 mg s.c. at Baseline, Weeks 1, 2, and 3, followed by administration every 4 weeks starting at Week 4.2
 - PsA patients, who have been previously exposed to TNF blockers, and/or with concomitant moderate to severe plaque psoriasis receive placebo as 2 (two) 1.0 mL PFS s.c..
 - Other PsA patients and axSpA patients receive placebo as 1 (one) 1.0 mL PFS s.c..
 - At Week 24, all patients in Group 2 will switch to their pre-assigned secukinumab treatment

Patients will receive study treatment at Baseline, Weeks 1, 2, and 3, followed by treatment every 4 weeks through Week 52 (last dose given at Week 48). At Week 24, patients originally randomized to placebo will switch to receive secukinumab 150 mg (1 injection of secukinumab 1 mL/150 mg) or secukinumab 300 mg (2 injections of secukinumab 1 mL/150 mg) in open-label fashion without a loading regimen. Blinding to the original treatment assignment will be maintained until after the Week 52 database lock and analyses are completed (see Section 5.4). Patients will self-administer all secukinumab and placebo doses as described in Section 3.1 at the study site or at home at indicated study visits (see Table 6-1) through Week 52.

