5.3 Treatment assignment and randomization

At Baseline, all eligible patients will be randomized via Interactive Response Technology (IRT) to 1 of the 2 treatment arms described in Section 5.2. The investigator or his/her delegate will contact the IRT after confirming that the patient fulfills all the inclusion/exclusion criteria. The IRT will assign a randomization number to the patient, which will be used to link the patient to a treatment arm and will specify a unique medication number for the first package of study treatment to be dispensed to the patient. The randomization number will not be communicated to the caller.

The randomization numbers will be generated using the following procedure to ensure that treatment assignment is unbiased and concealed from patients and investigator staff. A patient randomization list will be produced by the IRT provider using a validated system that automates the random assignment of patient numbers to randomization numbers. These randomization numbers are linked to the different treatment arms, which in turn are linked to medication numbers. A separate medication list will be produced by or under the responsibility of Novartis Drug Supply Management using a validated system that automates the random assignment of medication numbers to packs containing the study drug(s).

Patients will be stratified at randomization on the basis of PsA or axSpA disease. Based on enrollment target, it is planned that approximately 50% of randomized patients should be PsA

and approximately 50% axSpA patients to ensure a balanced patient population for the assessment of efficacy and safety.

Additionally, it is planned to enroll no more than 40% TNF-IR patients in the study.

The randomization scheme for patients will be reviewed and approved by a member of the Integrated Quantitative Sciences Randomization Group.

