5.6 Study completion and discontinuation

5.6.1 Study completion and post-study treatment

A patient will be considered to have completed the study when the patient has completed the last visit planned in the protocol i.e. Visit 18/Week 52 (see Table 6-1).

Information on the patient's completion or discontinuation of the study and the reason for discontinuation of the study will be recorded on the appropriate Study Phase Completion

eCRF page. In any case, the investigator or site staff must contact the IRT as soon as possible to record the patient's study completion and/or discontinuation.

The investigator must provide follow-up medical care for all patients who are prematurely withdrawn from or complete the study or must refer them for appropriate ongoing care. This care may include initiating another treatment outside of the study as deemed appropriate by the investigator. Based on the individual risk/benefit profile of a patient, treatment may be any non-biologic DMARD. In case of a biologic treatment, a waiting period of 3 months before initiating the treatment is recommended.

nr-axSpA patients with objective signs of inflammation at Screening, evident by either MRI with sacroiliac joint inflammation (according to source documentation) and/or hsCRP > ULN (as defined by central lab) who successfully complete the 1 year trial duration and were benefiting from secukinumab may be given the opportunity to enter an extension study. If an extension study is agreed on, it will be described in a separate extension study protocol.

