of $\geq 20\%$ [PsA patients]) or BASDAI of $\geq 20\%$ or ≥ 1 unit (0-10 scale) (axSpA patients, Pavy et al 2005) at Week 36 may be considered as a guidance for considering a patient inadequate responder to secukinumab treatment.

For patients who discontinue study treatment, a Dosage Administration Record eCRF should be completed, giving the date and primary reason for stopping study treatment.

The investigator must also contact the IRT to register the patient's discontinuation from study treatment.

If study drug discontinuation occurs because the treatment code has been broken, please refer to Section 5.5.9.

Patients who prematurely discontinue during Treatment Period 1 (secukinumab/placebo treatment from Baseline through Week 24) should return for assessments associated with Week 24 visit (4 weeks after the last study treatment in Treatment Period 1). Patients who prematurely discontinue during Treatment Period 2 (secukinumab treatment from Week 24 through Week 52) should return and complete assessments associated with Week 52 visit (4 weeks after the last study treatment in Treatment Period 2, see Table 6-1). The final visit should be performed before any new treatment is initiated.

Patients who prematurely withdraw from the study will not be replaced.

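### The contraception agreement in Protocol 10.2 lasts only as long as the study, which on its ordinary reading ends 12 weeks before the minimum period in exclusion criterion 13

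*Protocol*

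**What the plan says.** Protocol 10.2 (Informed consent procedures) sets out what women of child-bearing potential must be told and must accept before entry. They are told that the treatment "may involve unknown risks to the fetus if pregnancy were to occur during the study", and they agree that "they must adhere to the contraception requirement for the duration of the study". The section neither states a number of weeks nor defines when the study ends.

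Protocol 4.2, exclusion criterion 13, gives the contraception rule itself. Effective methods must be used while study treatment is being dosed "and minimum 16 weeks or longer if local label requires it (e.g. 20 weeks in EU) after stopping the study medication". Protocol 6.5.7 sends the reader to Section 4.2 for contraception.

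On timing, Protocol 5.2 has the "last dose given at Week 48". Protocol 5.6.1 treats a patient as having completed the study at the "last visit planned in the protocol i.e. Visit 18/Week 52". Under Protocol 5.6.2, a patient who stops early in the first treatment period returns for the Week 24 assessments "4 weeks after the last study treatment in Treatment Period 1", and the same 4-week interval applies in the second period.

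**The concern.** The contraception period has two end points in the same protocol. One is tied to the study and the other to the last dose. The study-based one stands in the section that governs what a woman is told and agrees to at consent.

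The sentence carries weight because Table 6-1 schedules no visit and no pregnancy test after Week 52. From then until the end of the criterion 13 period, contraception depends largely on what the woman understood and accepted at the start. Section 10.2 also makes the agreement a condition of entry, since a woman whose compliance is in doubt must not be enrolled. That condition needs a clear period. The people affected are those who draft, approve or verify consent, and through them the participants. The statistical analysis is not touched.

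**Working it through.** No design or power figure is involved. The check is calendar arithmetic on the visit schedule.

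**Inputs**
- Last dose for a completer: Week 48, Day 337 (Protocol 5.2, Table 6-1).
- Final visit for a completer: Week 52, Day 365 (Protocol 5.6.1, Table 6-1).
- Final visit for an early stopper: last dose + 4 weeks (Protocol 5.6.2 and Section 6).
- Contraception after the last dose: at least 16 weeks; 20 weeks as the EU example (Protocol 4.2, criterion 13).

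**Formula.** Let L be the week of the last dose and E the week in which the study ends for the patient. Shortfall = max(0, L + 16 − E), or max(0, L + 20 − E) on the EU example.

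**Ordinary reading: the study ends at the final visit**
- Completer, 16-week minimum: 48 + 16 = Week 64; 64 − 52 = 12 weeks. In days: 337 + 112 = 449; 449 − 365 = 84.
- Completer, EU example: 48 + 20 = Week 68; 68 − 52 = 16 weeks. In days: 337 + 140 = 477; 477 − 365 = 112.
- Early stopper: E = L + 4, so the shortfall is 16 − 4 = 12 weeks, or 20 − 4 = 16 weeks, whatever the value of L.

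**Importing reading: the words about the contraception requirement bring in criterion 13 whole**
- Agreement: 0 weeks short on either figure.

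**Sensitivity: the study is a fixed 52-week calendar for everyone (E = 52)**

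| Last dose (week) | Short of 16 weeks | Short of 20 weeks |
|---|---|---|
| 48 | 12 | 16 |
| 44 | 8 | 12 |
| 40 | 4 | 8 |
| 36 | 0 | 4 |
| 32 or earlier | 0 | 0 |

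The completer's figure is the same as on the ordinary reading. Only early stoppers differ. Twenty weeks is an example in criterion 13, not a ceiling, so a longer local label would widen each non-zero gap.

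**The case against.** The strongest reply is that there is one contraception requirement and 10.2 merely refers to it. The section gives no list of methods, no definition of who is covered and no number of weeks. All of that is in Section 4.2, where 6.5.7 also points. Nothing in 10.2 says that contraception may stop when the study ends, and a woman who follows criterion 13 also satisfies 10.2. Sites contact the randomization system only "after confirming that the patient fulfills all the inclusion/exclusion criteria" (Protocol 5.3), and monitoring fully verifies adherence to those criteria (Protocol 8.1). Pregnancy reporting under 7.6 covers any pregnancy after consent and states no end date.

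Much of this stands. The importing reading is reasonable, and criterion 13 governs eligibility either way. But 10.2 does more than refer: it attaches an end point of its own, and on ordinary reading that end point comes earlier. The checks in 5.3 and 8.1 concern eligibility, and 7.6 concerns reporting after a pregnancy has occurred. None of them tells a woman how long she is agreeing to use contraception.

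A reader might also infer that the fetal-risk clause contradicts criterion 13. It does not, because criterion 13 sets no period for fetal-risk information. That clause is narrower than it could usefully be, which is a drafting matter.

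In the other direction, one might try to stretch the study to the end of the SAE reporting window in 7.2.2. That window is a reporting period, and one of its limits is counted from the time the patient has stopped participating. It is not a meaning of study duration.

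**Conclusion.** The point holds as a wording inconsistency in the contraception agreement. If the study ends for a patient at her final visit, 10.2 stops 12 weeks before the criterion 13 minimum, and 16 weeks before it on the EU example. If 10.2 is taken to import criterion 13 in full, the agreement has no gap. The size therefore depends on how an undefined phrase is read, and the ordinary reading gives the larger figure.

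These are weeks of difference between two texts. A reader might take them as weeks of unprotected exposure, or conclude that women were misinformed. The documents support neither inference: criterion 13 applies throughout, and the consent form is a separate document that was not available. The alignment should be made because the requirement protects against fetal harm, no visit follows Week 52, and the correction is nearly free.

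**What to change.** In Protocol 10.2, replace the study-duration wording in the agreement with the criterion 13 period: throughout dosing and until at least 16 weeks after the last dose, or longer where the local label demands it, with 20 weeks in the EU as the example. As a conforming edit, extend the fetal-risk information in the same sentence to that period. Then check that the consent form states the same period.

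The cost is one amended sentence and one document check. No visit, pregnancy test, eligibility rule or SAP text changes.
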